2 INTRODUCTION

2.1 STUDY RATIONALE

Because existing approaches to manage FI are of limited efficacy,⁴ there is an unmet need for additional approaches to manage this symptom, which can have a potentially devastating impact on quality of life. A systematic review observed that while anal plugs might be helpful in some subjects, they are poorly tolerated, with a dropout rate ranging from 12.5% to 68% across the four studies³². Another device, the Renew anal insert device (Renew Medical Inc., Foster City, CA), is approved for treating FI in the United States. In the intent-to-treat analysis, 62% of subjects achieved ≥ 50% reduction in the frequency of FI

Protocol Number IRB-18-004642

with that device.⁷ The Minnesota Medical Technologies Anal Insert Device is designed to engage with and conform to the anorectal junction and the anal canal to provide an anatomical fit in order to protect against bypass leakage. The device is very soft and pliable which is expected to provide superior performance relative to devices which are currently on the market, with relatively few adverse events and good patient acceptance.

2.2 BACKGROUND

Fecal incontinence (FI) is a common symptom that can significantly impair quality of life.¹ FI, the involuntary leakage of stool from the anus, is a common symptom not only in nursing home residents, but also in the community. Almost one of 15 adult women have moderate to severe FI.²

Therapeutic options for FI include dietary modification and education, medications to manage bowel disturbances, pelvic floor retraining by biofeedback therapy, anal plugs, minimally invasive procedures (i.e., perianal injection of a bulking agent and sacral nerve stimulation), and surgery (e.g., anal sphincteroplasty).³ The approaches are of limited efficacy.⁴ The use of medications is often limited by constipation.

At present, FI is attributed to bowel disturbances, particularly diarrhea, anorectal dysfunctions, and pelvic floor injury.¹ Pelvic floor injury, which may result from obstetric injury, iatrogenic factors, is often irreversible and may manifest as a patulous anal canal.⁵ Anal plugs have been used to restore the anal seal. A Cochrane review identified 4 randomized cross-over or parallel studies of anal plugs, none of which are available in the United States.⁶ This review observed that while anal plugs might be helpful in some patients but are poorly tolerated, with a dropout rate ranging from 12.5% to 68% across the four studies. More recently, based on open label studies, an anal and a vaginal device have been FDA-approved for treating FI in the United States. For the Renew anal insert device (Renew Medical Inc., Foster City, CA), the intent-to-treat analysis observed that 62% of patients achieved \geq 50% reduction in the frequency of FI.⁷ 78% of users were extremely satisfied with the device. There were no serious adverse events and only 3 moderate adverse events (i.e., fecal urgency, soreness, and bleeding hemorrhoids).

Another device incorporates a vaginal insert and pressure-regulated pump.⁸ In the pivotal trial, 61 of 110 subjects completed successful fitting of the device. Of these, 78.7% achieved treatment success, defined as \geq 50% reduction of incontinent episodes at 1 month.

Because many women with FI [REDACTED]

[REDACTED] to FI. For example, while several small studies observed [REDACTED]

[REDACTED] we recently observed [REDACTED]

[REDACTED] There are no data on the [REDACTED] associated with FI. Hence we propose to explore these questions in this study.

2.3 RISK/BENEFIT ASSESSMENT

2.3.1 KNOWN POTENTIAL RISKS

Only subjects who satisfy stringent inclusion and exclusion criteria and provide written informed consent will be included in the protocol. Additional details as follows:

The Minnesota Medical Technologies Anal Insert Device is manufactured of biocompatible materials which are soft and pliable. The user interface has been designed such that use errors are either eliminated or reduced to the extent possible.

All study procedures are standard of care, with the exception of the study-specific physical examination and [REDACTED]

[REDACTED] assessment, additional questionnaires, [REDACTED] with study device inserted, subject self-insertion and evacuation of the MMT Anal Insert Device.

Anticipated risks for this study include:

- Mild discomfort
- Unexpected expulsion of the device
- New onset, or, if pre-existing, increased anorectal pain or discomfort
- Diarrhea
- Abdominal pain
- Anorectal irritation, pain, soreness
- Rectal, anal, or perianal infection
- Device over-insertion or device migration into anal canal or rectum
- Injury to anus, anal canal, or rectum
- New onset, or, if pre-existing, increased anorectal urge
- New onset, or, if pre-existing, increased abdominal gas
- New onset, or, if pre-existing, increased hemorrhoids or rectal bleeding
- New onset, or, if pre-existing, increased colonic obstruction or fecal impaction
- Perforation of anal canal or rectum
- Device breakage
- Discomfort, bruising, redness, swelling, bleeding around the site of the blood draw
- Feeling of lightheadedness when blood is drawn
- Infection at the site of the blood draw
- Rectal bleeding due to rectal catheter use
- Allergic reaction to materials of the testing equipment or study device

- If a researcher finds that results obtained from the [REDACTED] performed on patient [REDACTED], the subject will be contacted and [REDACTED].

There may be additional risks to subjects or embryos or fetuses in women who are of childbearing potential that are not known at this time. Any new significant information learned during this study that could impact a subject's decision to participate in the study will be communicated to the subject.

2.3.2 KNOWN POTENTIAL BENEFITS

There are no known benefits to the use of this device. Data gathered in this study may be of use in future treatment of subjects with fecal incontinence.

2.3.3 ASSESSMENT OF POTENTIAL RISKS AND BENEFITS

The Minnesota Medical Technologies Anal Insert Device is a device which has similar technical and biological characteristics with other anal inserts currently available for the treatment of FI.

Conservative treatments for FI include lifestyle changes, dietary modifications, bowel management programs (medications and enemas), and pelvic floor muscle exercises, physical therapy with or without biofeedback therapy.³⁰ These treatments have minimal risk.

Surgical approaches to treat FI are high risk solutions.

Anal inserts provide a conservative middle step in treatment options between alternative treatments such as lifestyle changes, medications, pelvic exercises, physical therapy, and surgical treatments.

3 OBJECTIVES AND ENDPOINTS

1. Primary: Primary Effectiveness Endpoint: A Relative Percentage Change in Episodes of Accidental Bowel Leakage (ABL) Determined by Comparing Treatment Results to Pre-treatment Results From the Baseline Period as Measured by Daily Diary Recordings . [Time Frame: Reduction in accidental bowel leakage from 4 week baseline period through 4 week treatment period (approximately Weeks 9-12).]

Measure Type	Primary
Measure Title	Primary Effectiveness Endpoint: A Relative Percentage Change in Episodes of Accidental Bowel Leakage (ABL) Determined by Comparing Treatment Results to Pre-treatment Results From the Baseline Period as Measured by Daily Diary Recordings.
Measure Description	This primary effectiveness endpoint will be calculated as a relative percentage

	of the baseline Accidental Bowel Leakage (ABL) using the following equation: % reduction in ABL = $100 * (\text{baseline period ABL} - \text{treatment period ABL}) / (\text{baseline period ABL})$
Time Frame	Reduction in accidental bowel leakage from 4 week baseline period through 4 week treatment period (approximately Weeks 9-12).

Secondary Efficacy Endpoint(s):

- The mean % reduction in Fecal Incontinence Severity Index (FISS) score from the baseline period to the end of the treatment period, calculated according to the following equation: % reduction in FISS = $100 * (\text{baseline period FISS} - \text{end treatment period FISS}) / (\text{baseline period FISS})$.
- The proportion of subjects in whom the frequency of FI episodes during the treatment period is greater than or equal to 75% lower than the frequency observed during baseline period.
- The proportion of subjects in whom, during treatment period, the device will reduce the number of days with FI by 50% as compared to baseline.
- The proportion of subjects in whom the device will reduce the volume of FI during treatment period as compared to baseline.
- The proportion of subjects in whom the Minnesota Medical Technologies Anal Insert Device reduces the proportion of FI episodes which are associated with diarrhea.
- The proportion of subjects in whom the Minnesota Medical Technologies Anal Insert Device reduces the number of episodes of passive and of urge FI
- The proportion of subjects in whom the Minnesota Medical Technologies Anal Insert Device improves the Quality of Life (QOL) related to FI during treatment as compared to baseline.
- The proportion of subjects in whom the Minnesota Medical Technologies Anal Insert Device will affect the composition of stool leakage during treatment as compared to baseline.
- The proportion of subjects are satisfied with the Minnesota Medical Technologies Anal Insert Device.
- The time for which a bowel movement can be deferred after the occurrence of urgency will be affected by the Minnesota Medical Technologies Anal Insert Device.
- The proportion of complete bowel movements will be affected by the Minnesota Medical Technologies Anal Insert Device during treatment as compared to baseline.
- Treatment with the Minnesota Medical Technologies Anal Insert Device will affect anxiety and depression during treatment as compared to baseline.
- The Minnesota Medical Technologies Anal Insert Device reduces the use of medications for FI during treatment as compared to baseline.
- Exploratory Endpoints:
 - Evaluate in up to [REDACTED] subjects the effects of the Minnesota Medical Technologies Anal Insert Device [REDACTED], as measured [REDACTED]
[REDACTED].

- - Evaluate if the effects of the Minnesota Medical Technologies Anal Insert Device on symptoms of FI [REDACTED], [REDACTED], [REDACTED], [REDACTED], and the acute effects of the Minnesota Medical Technologies Anal Insert device to prevent anal leakage.
- - Subjects [REDACTED] the Minnesota Medical Technologies Anal Insert Device [REDACTED].
- - Evaluate the [REDACTED] in subjects with FI
- - Investigate [REDACTED] associated with FI through [REDACTED] at baseline.

OBJECTIVES	ENDPOINTS	JUSTIFICATION FOR ENDPOINTS
Primary		
Investigate the effects of the Minnesota Medical Technologies Anal Insert Device on fecal continence in subjects with FI	1. Primary: Primary Effectiveness Endpoint: A Relative Percentage Change in Episodes of Accidental Bowel Leakage (ABL) Determined by Comparing Treatment Results to Pre-treatment Results From the Baseline Period as Measured by Daily Diary Recordings . [Time Frame: Reduction in accidental bowel leakage from 4 week baseline period through 4 week treatment period (approximately Weeks 9-12).]	Determination of substantial equivalence to predicate device.
Secondary		
Evaluate subject acceptance and ease of use of the Minnesota Medical Technologies Anal Insert device	
 • The mean % reduction in Fecal Incontinence Severity Index (FISS) score from the baseline period to the end of the treatment period. • The proportion of subjects in whom the frequency of FI episodes during the treatment period is greater than or equal to 75% lower than to the frequency observed during baseline period. • The proportion of subjects in whom, during treatment period, the device will reduce the number of days with FI by 50% as compared to baseline. • The proportion of subjects in 	

Protocol Number IRB-18-004642

OBJECTIVES	ENDPOINTS	JUSTIFICATION FOR ENDPOINTS
	
whom the device will reduce the volume of FI during treatment period as compared to baseline.
 
 • The proportion of subjects in whom the Minnesota Medical Technologies Anal Insert Device reduces the proportion of FI episodes which are associated with diarrhea. • The proportion of subjects in whom the Minnesota Medical Technologies Anal Insert Device reduces the number of episodes of passive and of urge FI • The proportion of subjects in whom the Minnesota Medical Technologies Anal Insert Device will improve the Quality of Life (QOL) related to FI during treatment period as compared to baseline. • The proportion of subjects in whom the Minnesota Medical Technologies Anal Insert Device will affect the composition of stool leakage during treatment period as compared to baseline. • The proportion of subjects are satisfied with the Minnesota Medical Technologies Anal Insert Device. • The time for which a bowel movement can be deferred after the occurrence of urgency will be affected by the Minnesota Medical Technologies Anal Insert Device. • The proportion of complete bowel movements will be affected by the Minnesota Medical Technologies Anal Insert Device during treatment period as compared to baseline. • Treatment with the Minnesota Medical Technologies Anal Insert Device will affect anxiety and depression during treatment period as compared to baseline. 	

Protocol Number IRB-18-004642

OBJECTIVES	ENDPOINTS	JUSTIFICATION FOR ENDPOINTS
	
 The Minnesota Medical Technologies Anal Insert Device reduces the use of medications for FI during treatment period as compared to baseline. 	
Evaluate the frequency of spontaneous expulsion of the Minnesota Medical Technologies Anal Insert Device during defecation, of involuntary expulsion, and of device migration into the rectum	Evaluation frequency rates	
Tertiary/Exploratory		

The Minnesota Medical Technologies Anal Insert Device will affect the amount of leakage [REDACTED].
 
Subjects [REDACTED] the Minnesota Medical Technologies Anal Insert Device [REDACTED].
	
 Evaluate the effects of the Minnesota Medical Technologies Anal Insert Device on [REDACTED] Evaluate [REDACTED] the Minnesota Medical Technologies Anal Insert Device on [REDACTED] [REDACTED], [REDACTED] and the acute effects of the Minnesota Medical Technologies Anal Insert Device to prevent leakage Evaluate [REDACTED] subjects with FI Investigate [REDACTED] with FI through [REDACTED] at baseline Observe subject [REDACTED] Minnesota Medical Technologies Anal Insert Device [REDACTED] 	Evaluation for potential future study.
Evaluate if the effects of the Minnesota Medical Technologies		

Protocol Number IRB-18-004642

OBJECTIVES	ENDPOINTS	JUSTIFICATION FOR ENDPOINTS
Anal Insert Device [REDACTED]		
Evaluate the [REDACTED] subjects with FI		
Investigate [REDACTED] with FI through [REDACTED] at baseline		

4 STUDY DESIGN

4.1 OVERALL DESIGN

This is a prospective, open-label, study during which 60 subjects with FI will be treated with the Minnesota Medical Technologies Anal Insert Device. Up to 150 subjects may be enrolled to ensure 60 subjects are eligible to participate in the Treatment Period. This study will consist of a baseline period and a treatment period. A fitting period, prior to the treatment period, will determine which of two devices sizes each study subject will use during the treatment period. Up to [REDACTED] of these 60 subjects will participate in a [REDACTED] sub-study to evaluate the effects of the Minnesota Medical Technologies Anal Insert Device on [REDACTED].

Subjects will sign the informed consent form at the screening visit. After signing the consent form, the subjects are considered enrolled in the study. At this visit, medical history and concomitant medications will be collected, as well as vital signs, and the ability of the subject to retain the device will be evaluated to determine eligibility for the study. Eligible subjects will proceed to baseline period (baseline bowel diary), during which subjects will record all bowel movements in a daily diary and complete questionnaires for 4 weeks. Subjects will be provided with a [REDACTED] and a [REDACTED] for use at home during the baseline period. Subjects will deliver, or send the [REDACTED] to the study site. Subjects who have 4 or more FI episodes during this 4-week baseline period will be eligible to continue to the fitting and treatment periods.

Subjects will return to the Mayo Clinic Rochester study site to have diaries assessed for compliance and eligibility for treatment and, if eligible, will complete quality of life questionnaire. Subjects eligible for treatment will be trained on the insertion and evacuation of the device and will be provided with instructions on how to contact [REDACTED] to have the devices shipped to them.

During this visit to the Mayo Clinic study site, subjects will receive the following assessments: baseline anoscopy (if not already performed within 6 months of informed consent), assessment of [REDACTED], a [REDACTED], and [REDACTED]. In up to [REDACTED] subjects who agree to participate in the [REDACTED] sub-study, [REDACTED] will be assessed [REDACTED].

Subjects who participate in the 2 to 4 week fitting period will insert the device after each bowel evacuation or expelling of the device, inserting only one device at a time and inserting a new device after each bowel evacuation or device expulsion. Subjects will be evaluated to determine which of two device sizes (10mm or 13mm) is preferred. Any changes in the use of device size will occur during the fitting period to ensure that the same size device is worn during the entire treatment period.

Subjects will proceed to a 4-week treatment period in which information on fecal incontinence, bowel habits, and global measures will be collected. Subjects will be asked to complete daily bowel diaries for 4 weeks during the Treatment period and to complete weekly questionnaires. After use, devices and applicators will be disposed of by subjects and not returned to the clinic, unless the subjects report concerns about the device function, in which case, subjects will be asked to return the expelled device to the clinic or directly to the sponsor, for device analysis.

While completing the treatment period of 4 weeks of daily diaries and weekly questionnaires, subjects will be asked to mail these diaries and questionnaires to the site on a weekly basis. At the end of the treatment period, subjects will be asked to complete additional fecal incontinence, quality of life and satisfaction questionnaires and mail them to the study site. Adverse events will be assessed between enrollment and study exit. Subjects will be asked to dispose of all unused devices and to confirm this with the study site.

After the treatment period, all individuals who withdraw for reasons other than personal preference (i.e., for medical reasons) and a minimum of 50% of all patients shall undergo an evaluation by anoscopy following the treatment period to assess for device related trauma.

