5 STUDY POPULATION

A sufficient number (up to 150) of subjects with a diagnosis of fecal incontinence in the general population of Mayo Clinic will be screened and consented for eligibility to participate in the study and to facilitate the enrollment of 60 subjects into the treatment period of the study. Of these, up to [REDACTED] [REDACTED] of the subjects will be recruited for the [REDACTED] sub-study.

The specific inclusion and exclusion criteria for enrolling subjects in this study are presented below. Exceptions to these inclusion and exclusion criteria must be discussed in advance and approved by the Principal investigator and sponsor. Any exemptions to the study entry criteria will be documented in the source documents and on the appropriate page of the case report form.

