5.5 STRATEGIES FOR RECRUITMENT AND RETENTION

All men and women aged 18 years and older will be eligible to participate regardless of ethnicity. The study may enroll up to 150 subjects until 60 subjects have been treated with the study device. Up to [REDACTED] subjects will be enrolled in the [REDACTED] sub-study. It is anticipated that that subjects will be recruited over 10-12 months from the outpatient clinic and patient databases at Mayo Clinic, Rochester and by public advertisement. Potential subjects may be approached by advertising, letter, phone, in person, or by e mail. All patient-facing materials will have sponsor and IRB approval prior to use. It is anticipated that the distribution of sex, race, and ethnicity will be consistent with the 2016 American Community Survey (ie, White (86.1%), African American (6.4%), Asian (7.1%), American Indian (0.8%), and other (1.6%).

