8 STATISTICAL CONSIDERATIONS

8.1 STATISTICAL HYPOTHESES

The hypotheses for the primary endpoints, which all apply to subjects with FI, are indicated below. For the primary study, these endpoints will be assessed for all 60 participants and separately for the 10 mm and 13 mm devices (versus baseline).

- 1. Primary Effectiveness Endpoint: A Relative Percentage Change in Episodes of Accidental Bowel Leakage (ABL) Determined by Comparing Treatment Results to Pre-treatment Results From the Baseline Period as Measured by Daily Diary Recordings . [Time Frame: Reduction in accidental bowel leakage from Baseline (Weeks 1-4) through Treatment period (approximately Weeks 9-12).]**

Measure Type	Primary
Measure Title	Primary Effectiveness Endpoint: A Relative Percentage Change in Episodes of Accidental Bowel Leakage (ABL) Determined by Comparing Treatment Results to Pre-treatment Results From the Baseline Period as Measured by Daily Diary Recordings.
Measure Description	This primary effectiveness endpoint will be calculated as a relative percentage of the baseline Accidental Bowel Leakage (ABL) using the following equation: % reduction in ABL = 100*(baseline period ABL - treatment period ABL) / (baseline period ABL)
Time Frame	Reduction in accidental bowel leakage from Baseline (Weeks 1-4) through Treatment period (approximately Weeks 9-12).

Secondary Efficacy Endpoint(s):

- The mean % reduction in Fecal Incontinence Severity Index (FISS) score from the baseline period to the end of the treatment period, calculated according to the following equation: % reduction in FISS = 100% (baseline period FISS - end treatment period FISS) / (baseline period FISS).
- The proportion of subjects in whom the frequency of FI episodes during the treatment period is greater than or equal to 75% lower than the frequency observed during baseline period.
- The proportion of subjects in whom, during treatment period, the device will reduce the number of days with FI by 50% as compared to baseline.
- The proportion of subjects in whom the device will reduce the volume of FI during the treatment period as compared to baseline.
- The proportion of subjects in whom the Minnesota Medical Technologies Anal Insert Device reduces the proportion of FI episodes which are associated with diarrhea.
- The proportion of subjects in whom the Minnesota Medical Technologies Anal Insert Device reduces the number of episodes of passive and of urge FI

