8.3 POPULATIONS FOR ANALYSES

Male and female, aged 18 and above, with a diagnosis of fecal incontinence. For the main and the sub-study, the analyses will follow the intent to treat (ITT) paradigm with all subjects randomized included in the analyses. Subjects with missing values for a particular endpoint will have their missing values imputed using the corresponding overall mean value from all subjects with non-missing data for that endpoint. An adjustment in the ANCOVA error degrees of freedom (subtracting one for each imputed value) will be made to account for the imputation. A similar adjustment for the Wilcoxon rank sum test (adjusting the degrees of freedom for the t-approximation) will also be examined. Similar analyses will be performed for the completer cohorts, i.e., all subjects who completed the 4 week treatment bowel diary and the [REDACTED] sub-study. For the bowel diary study, the modified ITT (mITT) cohort, which comprises those subjects who entered treatment and completed at least 1 week of device use will also be considered.

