8.4 STATISTICAL ANALYSES

8.4.1 GENERAL APPROACH

Male and female subjects aged 18 and above, with a diagnosis of fecal incontinence will be consented and screened for inclusion/exclusion criteria. It is anticipated that up to 250 subjects may be screened to result in 60 subjects that qualify via baseline diary data and can retain the device for inclusion in the Treatment Period of the study. Of these, [REDACTED] of the subjects will be recruited for the [REDACTED] sub-study at Mayo Rochester where [REDACTED] performed.

Outcome variables are summarized below.

Primary and secondary outcomes and other variables		
Primary Outcomes	Secondary Outcomes	Mechanism or Moderator Variables
1. Primary Effectiveness Endpoint: A Relative Percentage Change in Episodes of Accidental Bowel Leakage (ABL) Determined by Comparing Treatment Results to Pre-treatment Results From the Baseline Period as Measured by Daily Diary Recordings. [Time Frame: Reduction in accidental bowel leakage	
• A relative percentage change derived by comparing post-treatment Mayo Fecal Incontinence Severity Index (FISS) Scores to pre-treatment (End of Baseline Period) FISS Scores. [Time Frame: FISS score will be calculated at the end of the 4-week baseline period (Weeks 1-4) and the end of the 4-Week Treatment Period (approximately weeks 9-12).] In 50% of subjects, the FISS score will decline by ≥ 3 units.• The proportion of subjects in whom, during the treatment period, the frequency of FI episodes is greater than or equal to 75% lower than the frequency observed during the baseline period.	[REDACTED] [REDACTED]

Protocol Number IRB-18-004642

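### No efficacy population counts as a failure a subject who starts home device use in the fitting period and then stops

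*Combined protocol and SAP*

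**What the plan says.** **Device use.** Subjects use the device at home for at least two weeks in the fitting period (Sections 1.2 and 6.1.2). The schedule in Section 1.3 marks daily self-administration for both the fitting and the treatment period. Section 8.4.2 uses the fitting diaries to choose the size and sets them aside for efficacy.

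**Who is analysed.**
- ITT (Section 8.3): "For the main and the sub-study, the analyses will follow the intent to treat (ITT) paradigm with all subjects randomized included in the analyses". Section 6.3 describes the main study as within-subject controlled. Randomization appears only in the exploratory sub-study (Section 7.1).
- Modified ITT (Section 8.3): the cohort "which comprises those subjects who entered treatment and completed at least 1 week of device use will also be considered".
- Completers (Section 8.3): those who finished the 4-week treatment diary.
- Missing values (Section 8.3): replaced by the overall mean of subjects with data for that endpoint.
- Adverse-event withdrawals (Section 6.7): kept in the ITT safety summary, left out of the effectiveness summary.
- Section 8.1, on the primary endpoint: "these endpoints will be assessed for all 60 participants".

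**How the 60 are counted.**
- Section 4.1: "Up to 150 subjects may be enrolled to ensure 60 subjects are eligible to participate in the Treatment Period".
- Section 5: patients are consented "to facilitate the enrollment of 60 subjects into the treatment period of the study".
- Section 5.5: "The study may enroll up to 150 subjects until 60 subjects have been treated with the study device".
- Section 8.4.1: "60 subjects that qualify via baseline diary data and can retain the device for inclusion in the Treatment Period".

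**The concern.** Someone who uses the device at home and gives it up within two to four weeks has tried the treatment and not benefited. The plan has no place where that outcome counts against the device. Section 5.4 does not class such a subject as a screen failure either: its definition stops at withdrawal before the baseline diary and at fewer than four episodes in baseline. The subject is therefore an enrolled withdrawal with no defined role in the efficacy analysis.

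This matters because the protocol names poor tolerance as the weakness of anal plugs, with drop-out from 12.5% to 68% across four studies (Sections 2.1 and 2.2). An effect estimated mainly in those who stayed overstates what a patient offered the device can expect. Section 2.2 also shows how far the denominator can matter. In the vaginal-insert trial it cites, "61 of 110 subjects completed successful fitting of the device", and the 78.7% success rate is quoted among those 61.

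**Working it through.** **1. The plan's own figure.** Section 8.2 claims 90% power for an exact two-sided binomial test at 0.05, n = 30, 60% against 30%. The rule is success at 15 or more responders. The upper-tail error at 30% is 0.0169 and the power at 60% is 0.903. The stated figure reproduces.

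**2. Where a fitting quitter falls.**

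| Set or rule | Result for a fitting quitter |
|---|---|
| Modified ITT | Omitted: never entered treatment |
| Completers | Omitted: no treatment diary |
| ITT | Undefined: nobody is randomized in the main study |
| ITT, if read to include the quitter | Given the mean of subjects with data |
| Stopped for an adverse event | Left out of the effectiveness summary |

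No row scores the quitter as a failure.

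**3. Effect of mean imputation.** Assume 60 starters, 12 quitters and a mean reduction of 50% in the other 48.
- Plan's rule: (48 × 50 + 12 × 50)/60 = 50%.
- Quitters at no change: (48 × 50 + 12 × 0)/60 = 40%.

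Subtracting error degrees of freedom for imputed values, as Section 8.3 proposes, changes the precision and not this estimate.

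**4. Effect on the responder rate.** Section 8.4.1 expects 70% of subjects to have at least a 50% reduction. Assume that rate applies after treatment entry, that a share d of fitting starters quits, and that all of them are non-responders. The rate among starters is 0.70 × (1 − d). Filling 60 treatment places takes 60/(1 − d) starters, and 70% of 60 is 42 responders.

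| Assumed d | 0.70 × (1 − d) | Starters needed | Responders/starters |
|---|---|---|---|
| 10% | 63% | 67 | 42/67 = 63% |
| 12.5% | 61% | 69 | 42/69 = 61% |
| 20% | 56% | 75 | 42/75 = 56% |

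**5. Effect on the test against 30%.** The sizing rate of 60% becomes 0.60 × (1 − d). With 60 starters the rule is 26 or more responders.

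| d | Diluted rate | Power, 60 starters | Power, 30 starters |
|---|---|---|---|
| 0 | 60% | 0.997 | 0.90 |
| 10% | 54% | 0.96 | 0.73 |
| 12.5% | 52.5% | 0.94 | 0.68 |
| 20% | 48% | 0.80 | 0.48 |

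If 42 responders are observed among 75 starters, the exact two-sided p-value against 30% is about 0.000003.

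**6. The cited vaginal-insert trial.** 78.7% of 61 is 48 subjects, and 48/110 = 43.6% of those who attempted fitting.

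**The case against.** A reader might infer that fitting quitters are replaced and fall outside every efficacy denominator. The documents do not establish either.
- **Replacement.** Only Section 5 clearly counts the 60 at entry to the treatment period. Section 4.1 counts those eligible for it, and eligibility turns on the baseline diary and on exclusions applied in baseline or at the visit that follows (Sections 4.1 and 5.2). Section 8.4.1 counts on baseline diary and retention, both settled before fitting. Sub-study subjects are drawn from the 60 and are assessed before fitting. The only express rule for replacing withdrawals (Section 5.4) concerns the sub-study, and it keeps them in ITT.
- **Every denominator.** An undefined ITT set is not one that excludes quitters. The modified ITT is listed in addition to ITT, which suggests that ITT was meant to be wider.

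A reader might also see the fitting period as a screen that removes non-tolerators. It is not one by design: every branch of the size algorithm leads to treatment, including a reduction below 75% with poor comfort scores. Only withdrawal takes a subject out.

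Larger dilutions are tempting too. Using 49/110 as the quit rate gives 0.70 × 61/110 = 39%, but that share comes from a different type of device. Using 68% gives 22%, but this needs 60/0.32 = 187.5 starters, above the cap of 150 enrolled. The 12.5% to 68% figures are overall drop-out rates for other plugs, not fitting-period rates.

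Finally, no test is planned against the predicate's 62%, and the documents do not say where that ITT count began. A claim that the two figures are not comparable therefore cannot be proved from them.

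All of this stands, and it limits the point. None of it makes a fitting quitter count as a failure. Left out, the subject is ignored; kept in ITT, the subject receives the average of those who stayed.

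**Conclusion.** The point holds in this form: no efficacy population is defined so that a fitting quitter counts as a failure, and both explicit rules that could reach such a subject (mean imputation and the adverse-event exclusion) favour those who tolerated the device. Whether quitters are replaced is unclear, because the four statements of the target of 60 do not agree.

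The size depends on a quit rate that the documents do not give. For quit rates of 10% to 20%, a 70% responder rate falls by 7 to 14 percentage points when all fitting starters are counted. This assumes that the 70% applies after treatment entry and that every quitter is a non-responder. The 39% case is illustrative only, and the 22% case should not be used.

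The main harm is to the size of the reported effect. With 60 subjects, significance against 30% is little affected at low quit rates. An analysis by device size with about 30 subjects has less room. The plan should be changed, but the design need not be.

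**What to change.** - **Section 8.3:** define the main-study ITT set as all subjects who start home device use in the fitting period. Count those who stop before or during treatment for an adverse event, discomfort, expulsion or lack of effect as non-responders for the proportion endpoints, and as 0% reduction in the ITT analysis of the primary endpoint, in place of overall-mean imputation. State a rule for stops with other causes. Zero reduction is one reasonable convention; what matters is that it is fixed in advance.
- **Section 6.7:** keep adverse-event withdrawals in the ITT effectiveness analysis. Otherwise this section contradicts the new set.
- **Modified ITT:** keep treatment entry plus at least one week of use, labelled as such.
- **Sections 4.1, 5, 5.5 and 8.4.1:** state one counting point for the 60. If enrolment continues after a fitting withdrawal, that subject stays in the ITT denominator.
- **Reporting:** give the numbers starting and completing fitting, with reasons for stopping, next to the primary result.

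The cost is wording in these sections and one extra table. The analysis change itself needs no added patients or procedures. The downside is a less favourable headline ITT percentage.
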